H2: Behavioral intent has a direct positive association with both the frequency and the duration of the LN/EP mobile app use.

H3: eHealth literacy and smartphone experience moderate the association between behavioral intent antecedents (performance expectancy, effort expectancy, and hedonic motivation) and behavioral intent. Low eHealth literacy and smartphone inexperience will weaken the association between the antecedents and behavioral intent.

5.0 Explore: a) associations of baseline antiretroviral treatment (ART) adherence with characteristics such as demographics, self-reported behaviors and symptoms, health literacy, access to care, disease progression, comorbidities, and substance use in a randomized interventional study of HIV and mobile application technology in rural Georgia.

H1: Participants changing ART medication regimen or those that have developed new resistance are different than those starting ART.

b. Preliminary Studies

This project effectively builds on the NIH/NINR funded pilot study (R21 NR010862) in which we developed and tested the LN in a large urban HIV clinic that serves primarily low income, African American clients diagnosed with AIDS. Prior to developing the LN songs, we conducted a music preference survey of 135 patients from the Grady Health System Infectious Disease Program, the site for the urban pilot project, who had been on ART for at least 6 months. This survey posed questions about music genre preferences, a ranking of top preferences, whether they own an MP3 player, demographics, and prescribed ART. 76% of the participants were between 40-59 years old, 86% were African American, and 59% owned an MP3 or personal CD player. The top 10 genres used to develop the LN are in order: Gospel, Rhythm and Blues (R&B), Oldies, Hip-hop, Motown, Smooth Jazz, Easy Listening, Soul, Blues, and House.

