RCT: Sources of information will include baseline, 3, 6, and 9- month follow-up assessments and tracking of usage of mobile app conducted solely for the purpose of this research. Assessments will include assessments of adherence to antiretroviral medications and, measures of symptoms, depression, self-efficacy, attitudes, goals, demographic information including substance use, and health literacy. Physiologic measures will include ART drug levels in a small hair sample (100 strands) cut from the occiput (back of head) at each time point. Lab results for CD4, viral load, and drug resistance will be extracted from medical records consistent with the study time points. Study assessments will be conducted in person using ACASI coincident with provider appointments. They will last about 3 hours. Monthly unannounced pill counts will be conducted via smart phone using the camera and pill count survey within app with assistance from the clinical research coordinator as needed. As part of our reliability testing, up to 60 participants will be asked to repeat their pill count about 24 hours after baseline. Hair samples will be collected in person by study personnel on-site at each time point. Tracking usage of the app will be done via the mobile web application which will send messages to the HIPAA compliant server each time a participant uses the app. Participants will be assigned to one of two conditions: an educational music program (EP) or the LN treatment condition. All participants will receive the usual care at their respective HIV care agencies. Evaluation information will be obtained about the satisfaction and use of the programs at the end of the RCT study. The option of 3, 6, and 9 month follow up study assessments administered via phone call will be offered to participants who are unable to complete in person visits. If this option is elected the hair sample and visual analog scale data will not be collected.

d.1.b Other interactions

Participants will receive reminder calls and text messages regarding study appointments. Text messages will also remind them to listen to the LN & EP.

d.2 Respondent burden

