h.2.b Analysis Initial analysis will include descriptive statistics of sample characteristics (demographics, substance use, depression scores, etc. and CD4 and Viral Load.) and psychometric evaluation of all scored instruments. A combination of statistical software will be used for statistical analysis and data visualization, including SPSS (v.19), SAS (v. 9.2), and R (v. 2.13). Distributions, potential outliers, and patterns of missing data will be assessed to assure that the data meet assumptions for subsequent inferential tests. Missing data imputation methods may be used for small amounts (<5%) of missing data such that missing data are random. All statistical tests will be performed at the 5% level of significance, with exact p-values reported. Intent-to-treat procedures will be employed. For non-normal data, transformations may be performed to improve deviations from normality. However, it is well known that PC, viral loads and adherence measures are often skewed and experience floor and/or ceiling effects. Therefore, generalized linear models (GLM)/generalized estimating equations (GEE) frameworks will be employed as a more accurate reflection of the true underlying distributions generating these data. It is expected that logistic (logit)³⁷ and log-gamma³⁸ may be appropriate as well as Poisson, zero-inflated Poisson, and other link functions.^{39, 40} Additionally, it is expected that some attrition over time will occur. Mixed/multi-level models (MLM) will be used instead of repeated measures analysis of variance (RM-ANOVA) methods since MLM uses all available data (does not delete cases with missing values over time), handles data that are missing at random (MAR) which RM-ANOVA cannot, does not assume independence across time, provides a breakdown of variance both within and between subjects, and allows for both time-invariant and time-varying covariates.^{39, 40} It is expected that the majority of the analyses will occur in SPSS. However additional MLM and GLM/GEE models will be run using SAS (PROC MIXED, PROC NLINMIXED) and R (packages: LME4, GAMLSS as well as BRugs, which employs Bayesian estimation methods.⁴¹⁻⁴³

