Satisfaction (Aim 1) Two assessments will be conducted and analyzed to determine participant satisfaction with the mobile app in general, LN program and interactive manual. Both times, we will ask questions about likeability, usage rates, ease of use, acceptability, satisfaction, relevance, favorite song, understandability, and suggestions for improvement. The first assessment will entail observations and discussions with rural PLWHA while using the mobile app in focus group format. Observations and discussions will be recorded and content analyzed for themes, which will inform final revisions to the LN app. The second feasibility analysis will be the Program Evaluation Survey at the end of the study. Scaled responses to questions related to the above criteria will be analyzed using descriptive statistics and written comments will be entered into nVivo software and content analyzed for themes. We will also describe and evaluate the usage data from the web application designed to track app usage. We will determine average usage patterns and compare between groups (LN vs. EP).

Outcomes (Aim 2) All covariates will be evaluated to determine if any differences exist at baseline between the 2 groups (LN and EP), as well as testing for interactions (moderation) between groups and time. Inter-correlation among the covariates will also be evaluated. Multicollinearity diagnostics (variance inflation factors, tolerance, condition index) will be used to determine which covariates should remain in the subsequent models. MLM longitudinal models as detailed above will be used for each outcome (H1: adherence, H2: drug levels, and H3: CD4, viral load, drug resistance) to test differences between the 2 groups (group main effect), test for changes/differences from baseline to 3, 6 and 9 month (time main effect) and test for group by time effects (i.e. changes from baseline that are differences between the 2 groups) adjusting for significant covariates/moderators as needed. Appropriate link functions (e.g. logit, Poisson, other) will be assessed for each outcome within the MLM.

Exploratory outcome, mediators and moderators (Aim 3) Symptoms and symptom management scores will be examined using MLM as described above. Self-efficacy, outcome expectancy and personal goals are mediators in our model and meet the criteria for mediators as defined by Baron and Kenny⁴⁴

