and Bennett.⁴⁵ First, the intervention is designed to foster change in self-efficacy, outcome expectancy, and personal goals, and second, the mediators, in turn, are associated with the outcomes of adherence and symptoms. A number of authors have explicated the process by which mediation can be tested.^{46,47} A combination of statistical methods will be employed to determine the significance of mediation effects through the SPSS macro as described in Preacher and Hayes.⁴⁸ This SPSS macro runs the Baron and Kenny method and Sobel⁴⁷ test, as well as a non-parametric bootstrapping estimate, which is a more rigorous alternative to the Sobel test of the indirect effects. Based on the outcomes of these tests, each potential mediator will be assessed as to whether it provides for total, partial, or no mediation effect. Moderators such as depression and health literacy will be tested for main effects (differences at baseline) as well as for interaction (moderation effect) with the intervention (group) and across time. These moderation effects will be included within all mediation models to assess the extent of mediation of self-efficacy and outcome expectancy on adherence outcomes after adjusting for moderators and covariates.

Smartphone acceptance (Aim 4) Multivariate regression models will be used to address each hypothesis related to this aim. For Hypothesis 1, each antecedent (effort expectancy, performance expectancy and hedonic motivation) will be tested as a significant predictor of behavioral intent after adjusting for potential demographic covariates, such as age and gender. For Hypothesis 2, a simple regression model will assess the amount of association between behavioral intent and LN/EP app usage. For Hypothesis 3, multivariate regression will again be used to test for the moderating effects (i.e. two-way interaction effects) of smartphone experience and eHealth literacy on the association between the antecedents and behavioral intent. In place of traditional regression methods, the PROCESS plug-in macro for SPSS⁴⁹ will be employed using methods outlined by Hayes⁵⁰ to test the moderation effects of both smartphone experience and eHealth literacy on behavioral intention. (Note: for a continuous predictor variable and a continuous moderator variable, each will be mean-centered using the PROCESS macro before computing the interaction variable to avoid mathematically induced multicollinearity issues present for moderation testing.)

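### Aim 4 H2 regresses app usage on behavioral intent across LN and EP users with no term for randomised arm, so if the two apps differ in both variables the pooled slope is not the within-app association

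*Combined protocol and SAP*

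**What the plan says.** The hypothesis, under Specific Aims (Aim 4, H2), is: "Behavioral intent has a direct positive association with both the frequency and the duration of the LN/EP mobile app use". There are thus two usage outcomes, and the two apps are written together.

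The analysis is in section h.2.b, Smartphone acceptance (Aim 4). The paragraph opens: "Multivariate regression models will be used to address each hypothesis related to this aim". For H1 it tests each antecedent "after adjusting for potential demographic covariates, such as age and gender". For H2 it says that "a simple regression model will assess the amount of association between behavioral intent and LN/EP app usage". For H3 it returns to multivariate regression with interaction terms. Randomised arm is not named for any of the three hypotheses, whether as a covariate, an interaction or a stratification factor.

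Three other places bear on this:

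- Section d.2.1 defines the arms: "Participants will be assigned to one of two conditions: an educational music program (EP) or the LN treatment condition".
- Section h.2.b, Satisfaction (Aim 1), says of app usage: "We will determine average usage patterns and compare between groups (LN vs. EP".
- The opening paragraph of section h.2.b provides for distribution checks and adds: "For non-normal data, transformations may be performed to improve deviations from normality". It also lists other link functions, including Poisson and zero-inflated Poisson. The reason given for these is that "it is well known that PC, viral loads and adherence measures are often skewed"; app usage is not mentioned there.

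**The concern.** LN and EP differ in content. Intent to use an app, and actual use of it, could both depend on which app a participant was given. The plan treats an arm difference in usage as an open question under Aim 1 but does not carry it into H2.

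If one app produced both higher intent and higher use, a regression across all participants would show a positive slope even when, among users of either app, intent predicted nothing. If the differences ran in opposite directions, a real association could be weakened or hidden. H2 asks whether a person's intent leads to use, and Aim 4 is meant to guide refinement of the intervention. A slope driven by which app people received would answer a different question.

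The paragraph also leaves the analyst unsure what to fit, since it promises multivariate models for every hypothesis and then describes a simple one for H2.

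**Working it through.** **No figure to reproduce.** The plan gives no sample size, power or effect size for Aim 4. The inputs taken from it are 200 participants, 100 per arm (section h.1), and the 5% level (section h.2.b). I assume two-sided tests. The arm shifts in intent and usage are my assumptions, because the documents give none.

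**Pooled correlation produced by arm alone.** Let dI and dU be the arm shifts in intent and usage, in within-arm SDs, with 1:1 allocation and no association within either arm. Then

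r = (dI × dU / 4) / √[(1 + dI²/4)(1 + dU²/4)].

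For dI = dU = 0.5: r = 0.0625 / 1.0625 = 0.059. A rough test statistic is r√N = 0.0588 × 14.14 = 0.83. The chance that it passes ±1.96 is about 13%.

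**Simulation** (10,000 replicates per row, normal data, N = 200, no within-arm association; the last two columns give the proportion of trials with a significant slope):

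| dI | dU | pooled r | no arm term | with arm term |
|---|---|---|---|---|
| 0 | 0.5 | 0.000 | 4.8% | 5.0% |
| 0.5 | 0 | 0.000 | 5.1% | 5.0% |
| 0.2 | 0.5 | 0.024 | 6.6% | 5.3% |
| 0.4 | 0.4 | 0.038 | 8.4% | 5.0% |
| 0.5 | 0.5 | 0.059 | 13.5% | 5.2% |
| 0.5 | 0.8 | 0.090 | 24.5% | 5.2% |
| 0.8 | 0.8 | 0.138 | 50.1% | 5.1% |
| 0.5 | −0.5 | −0.059 | 13.0% | 5.1% |

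With all 240 enrolled participants, the 0.5/0.5 row becomes 15.1% without arm and 5.2% with it.

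**Masking.** With a within-arm correlation ρ, the numerator of r becomes ρ + dI × dU / 4. Take ρ = 0.2 as an illustration, with shifts of 0.5 and −0.5. The pooled value is (0.2 − 0.0625) / 1.0625 = 0.129, so a positive association looks about a third smaller.

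**Does the usage scale matter?** I repeated the exercise with overdispersed count usage (gamma-Poisson, dispersion 1, mean 20 in the lower arm, N = 200, 8,000 replicates), changing the scale and the arm term separately:

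| Intent shift | Usage ratio | raw, no arm | log(1+usage), no arm | raw, arm | log(1+usage), arm |
|---|---|---|---|---|---|
| 0.5 SD | 1.5 | 9.7% | 8.5% | 4.9% | 5.2% |
| 0.5 SD | 2 | 17.8% | 15.0% | 5.2% | 5.2% |
| 0.8 SD | 2 | 34.6% | 30.4% | 4.8% | 5.0% |

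The arm term alone brings the rate back to about 5% on either scale; the log scale without it does not. With intent unrelated to usage and no arm shift, linear regression rejected in 5.2% of trials for zero-inflated negative binomial usage and 5.4% for lognormal usage.

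**The case against.** The strongest reply is that the artefact needs two things the documents do not establish: an arm difference in usage and an arm difference in intent. Planning to compare usage between groups does not show that it differs, and nothing in the text says that intent does. The text also does not say when intent is measured; the table of measures is in the IRB application. If intent is collected before randomisation, no systematic arm difference is expected, chance imbalance aside, and the mechanism falls away. Small shifts do little harm: 0.2 SD in intent with 0.5 SD in usage gives 6.6%. All of this stands, and it makes the concern conditional.

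It can also be said that the opening sentence on multivariate models leaves room for covariates in H2, and that pooling is the natural reading of the combined LN/EP wording but is not stated outright. Both are fair. They show that the text needs to be settled; they do not supply an arm term.

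A reader might go further and infer that the plan commits to a plain linear model for skewed usage, and that this contributes to the false positives. The documents do not support that. Simple most naturally means one predictor, no distribution or link is named for usage, and the general analysis paragraph allows transformations and other link functions. The second table shows that the scale is not the cause. A reader might also infer that arm is known to affect both variables, so that H2 is certainly confounded. That is an assumption; the documents support only that it could be.

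**Conclusion.** The concern holds in a limited, conditional form. As written, H2 is a one-predictor regression across both apps with no arm term, in tension with the paragraph's own opening sentence. If the apps differ in both intent and usage, the pooled slope is not the within-app association. For same-direction shifts of 0.4 to 0.8 SD in both variables, the false-positive rate at N = 200 is about 8% to 50%; a shift in one variable only leaves it at about 5%. These figures rest on assumed shifts, two-sided testing and no true within-app association.

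The simple model applies to H2 only. H1 and H3 are multivariable; they also name no arm term, but no inflation was calculated for them. The point is minor: Aim 4 concerns acceptance and use of the app, and the randomised Aim 2 comparison does not depend on it.

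**What to change.** In section h.2.b, Smartphone acceptance (Aim 4):

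- Replace the simple regression for H2 with a model that includes randomised arm, applied to both frequency and duration of use. This also settles the conflict with the opening sentence.
- Add an intent-by-arm term to H2, and report the slope for each app if the slopes differ.
- Add arm to the H1 and H3 models for consistency.
- State when behavioral intent is measured relative to randomisation.

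No particular distribution for usage need be imposed. It can follow the checks, transformations and link functions that section h.2.b already provides for, with a sentence saying that these apply to app usage as well.

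The cost is a few lines of text and one or two degrees of freedom from about 200. No extra data are needed, since arm is known for every participant.

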All clinics are in the Georgia Public Health System, receive Ryan White funds, have access to the AIDS Drug Assistance Program (ADAP), and provide HIV care and medications. According to 2009 data the Coastal District in Savannah has the highest number of PLWHA (2829) outside the Atlanta MSA and is Georgia's third largest Ryan White provider. It is followed by the East Central District in Augusta (2540). Other sites are the North Central District in Macon (2286), and Northeast District in Athens (811) and Columbus (1388). These agencies cover the northeastern, southeastern, and central parts of Georgia and represent 54 (34%) of the state's 159 counties. Of the 54 counties represented in these districts, 40 (74%) have a population of <35,000; 52 (96%) were designated as medically underserved areas (MUA) or populations (MUP); and 47 (87%) were designated as Health Professional Shortage Areas (HPSA's) by the US Health Resources & Services Administration in 2009. The clinics serve a vulnerable group. Each clinic serves a majority of African Americans who are at or below the poverty level. We will be hiring a local study site coordinator who will be trained by the project coordinator to conduct all study activities at each site. This will ensure culturally appropriate research site coordinators who understand the people and locale. It will also eliminate any burden on the site staff.

c. Recruitment

c.1 Site: Participants will be recruited from each site by the local study site coordinator.

c.2 Methods: Posters and fliers will be posted at each study site and given to site staff for distribution. Potential participants will be referred by providers, case managers, nurses at the sites and may also self refer. Potential participants will receive written materials about the study and will be

[figure not shown]
asked if interested. Study staff will be trained to deliver a presentation briefly explaining the study and answering questions about the study.

c.3 Materials: These are to be developed and will be forwarded when completed.

c.4 Monitoring: Our goal is to recruit a total of 10 persons for the focus groups (3-5 from 2-3 sites) and 240 for the main study. For the main study, our goal is about 10 persons per month (from all sites). We will assess recruitment progress monthly. If recruitment falls short we will add additional sites. If we remain behind we will expand eligibility criteria to include all persons on ART.

d. Procedures

d.1 Study design

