Men and women who meet the study criteria will be recruited at the HIV Clinics described above. Site coordinators will be trained to deliver a presentation briefly explaining the study and answering questions about the study. Potential participants will receive written materials about the study and will be given a phone number to call. Individuals who are interested in participating will be given a screening assessment to assess eligibility. Before the screening assessment, the study will be explained in detail including the purpose of the study, the participant's role in the study, study requirements, and time commitments, confidentiality and privacy protections (including for focus groups and RCT), and questions will be answered. Potential participants will be assured that their care at the clinic will not be affected in any way by their decision whether or not to participate in the study. They will be given an opportunity to ask questions and receive additional explanation. The consent form includes an explanation of the study, the risks and benefits of participation, the duration and type of participation, description of the procedures, contact person for the research including the chair of the IRB, the voluntary nature of participation, and the right to withdraw without penalty will be read and explained. Since this population is at risk for cognitive impairment that, in some cases, may limit capacity to provide consent, a consent post-test will be administered to evaluate understanding of study procedures, risk/benefits, etc. If this is completed with 100% accuracy, they will be asked to sign an informed consent form, and given a copy of the form for their records. For focus groups, the group will begin thereafter. For the RCT, they will next complete the BSI screening and if the results of the screening assessment indicate that they are eligible for the study, they will be given an invitation to participate. They will then begin the baseline assessment.

f.2.b. Protections Against Risks

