The target sample size is 200 participants with 100 allocated to each group. Taking into account projected attrition of about 40 persons, we expect a final sample size of 240. Given our approach using multi-level longitudinal models (MLM) for these 200 subjects, 2 groups at 4 time points, we are 95% confident that power levels between 84% to 98% will achieve minimal detectable differences of 0.4 (within time and group by time) and 0.5 (between groups) (small-to-moderate effect sizes) for random effects subjects variance equal to 1. Covariate adjustments should further reduce variability and detectable effect sizes while increasing power. Additionally, to address the differences in proportion achieving virologic suppression and drug resistance, a chi-square test for a sample size of 200 yields a small-to moderate effect size (ω) of 0.1981 for 1 degree of freedom (2 x 2 table) at 80% power and 5% level of significance.

h.2 Plans for data management and analysis

h.2.a Data management Procedures for data management and monitoring will be initiated during the start-up phase. The project coordinator will coordinate the organization and processing of forms, and schedule and implement checks of data quality and completeness. Data from the ACASI files will be saved in the QDS data warehouse. Data will be backed up on a regular basis to prevent loss of data. Data will be transferred electronically from the sites to a secure password protected, HIPAA-compliant server at Emory University. A data-checking plan based on each questionnaire will be used to look for suspicious entries. Data monitoring will include scheduled checks for completeness every 2-4 weeks. Data sets from all assessment points will be merged as necessary to answer the research questions. Personal goals will be reported by the participant and typed into the database for qualitative analysis. They will be analyzed for the dimensions of content, specificity, effectiveness, and control. [name] will oversee the final quality assurance/quality control data reviews. She will design and conduct the statistical analyses; assist as with designing research forms and data entry; and collaborate with the

investigators on analysis and interpretation. We have successfully used these procedures with the pilot project and other research projects.

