Exploratory outcome (Aim 5) Analysis includes the first 106 participants in the main study and participants are compared based on their inclusion criteria (participants switching ART medications because of new resistance (non-adherence) vs those starting or switching ART medication for non resistance reasons or toxicity). Data will be de-identified by the Rural Music Project data manager prior to analysis. The data manager will not conduct any data analysis for this aim. Baseline ACASI data will be merged with inclusion criteria data from site tracking log based on the participant identification number and analyzed using SAS (v. 9.4) statistical software.

3. Training research personnel

Interviewer training Experienced interviewers will be trained to conduct baseline and follow-up interviews. To control for measurement error, we will be using ACASI to administer most of the items. Interviewers will also be trained in hair sample collection, processing, and storage. This process will be standardized based on the equipment and procedures. We will develop procedures manual which includes all the important elements of interviewing along with specific information related to each item on the questionnaires/surveys, as well as written procedures for hair sample collection, processing, and storage. This manual will serve as the basis for training. Interviewers will use standardized scripts to introduce the participant to the study and explain the questionnaires/surveys, and procedures. The interviewers will practice the survey, screening, baseline, and follow-up scripts with each other. They will practice hair-sampling procedures on models. Weekly meetings and contact with the PI will be held to discuss problems and issues that may arise.

Focus group facilitator training Two focus group facilitators will conduct the groups. They will be trained in group dynamics and how to ask general questions and more specific questions. They will use a script written by the PI and Co-I to elicit comments about the LN app and smart phone use.

4. Plans for data management and monitoring

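### Aim 5 is limited, with no stated reason, to the first 106 participants, although the baseline data it uses are collected on all 240 planned (minor; exploratory aim)

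*Combined protocol and SAP*

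**What the plan says.** The Aim 5 paragraph of h.2.b fixes the analysis set: "Analysis includes the first 106 participants in the main study and participants are compared based on their inclusion criteria". It compares people who switched because of new resistance with people who started ART or switched for another reason. The data are the baseline ACASI interview, linked by participant number to the entry criterion in the site tracking log. No follow-up data are used. The paragraph does not say why 106 was chosen, what date it corresponds to, or whether the analysis is repeated when enrolment closes.

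The aim itself (Specific Aims, 5.0) carries no such limit. It seeks associations of baseline adherence with participant characteristics "in a randomized interventional study of HIV and mobile application technology in rural Georgia".

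On numbers, c.4 Monitoring plans 10 focus-group volunteers "and 240 for the main study". Section h.1 says "The target sample size is 200 participants with 100 allocated to each group" and then "Taking into account projected attrition of about 40 persons, we expect a final sample size of 240".

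On data collection, d.2.1 says of the trial: "Sources of information will include baseline, 3, 6, and 9- month follow-up assessments". Section f.2.a, after consent and screening, says: "They will then begin the baseline assessment". The telephone alternative in d.2.1 is offered for the 3, 6 and 9 month assessments, not for baseline.

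On changes during accrual, c.4 says "If recruitment falls short we will add additional sites", and if accrual still lags, eligibility widens to everyone on ART. The current criteria in a.2 already list a detectable viral load, and simply being on ART, alongside starting or changing a regimen.

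**The concern.** A baseline-only question does not have to stop at an early subset. Every later participant gives the same interview and has an entry reason recorded, so leaving them out lowers precision for no stated benefit. The first 106 by enrolment order are also not a random sample of the trial. If sites or eligibility changed afterwards, an answer from the 106 may not describe the population that the aim names. At stake are the precision and coverage of one exploratory, non-randomised analysis.

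**Working it through.** **Inputs.** Aim 5 set 106 (h.2.b). Planned enrolment 240, with about 40 expected losses, leaving 200 (c.4, h.1). Accrual goal about 10 a month (c.4). Significance level 5% (h.2.b), taken as two-sided because the sides are not stated. Power of 80% is borrowed from the chi-square statement in h.1; the plan sets none for Aim 5. Group splits are assumptions, since the documents give no Aim 5 group sizes.

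**1. The plan's own figures.** Detectable w for 200 people on 1 df: (1.960 + 0.8416)/√200 = 2.8016/14.142 = 0.1981, as stated in h.1. Enrolment: 200/(1 − 40/240) = 240, also as stated. The 106 has no stated derivation to reproduce.

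**2. Denominator.** The expected losses occur after baseline, so they do not reduce the baseline data. The right comparison is with 240, not 200. (Against 200 the unused share would be 94/200 = 47%.)

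**3. Share left out.** 240 − 106 = 134, and 134/240 = 55.8%. At the goal rate, 106 people are the first 106/10 = 10.6 of 240/10 = 24 months.

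**4. Association analysis.** This needs no grouping by entry reason. Standard errors scale with 1/√N, so the ratio is √(240/106) = 1.50. This assumes that the same fraction of records is usable in both sets.

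**5. Two-group comparison.** Detectable standardised difference = 2.8016 × √(1/n₁ + 1/n₂). For 30/70:
- N = 106: 2.8016 × √(1/31.8 + 1/74.2) = 0.59
- N = 150: 2.8016 × √(1/45 + 1/105) = 0.50
- N = 240: 2.8016 × √(1/72 + 1/168) = 0.39

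The same formula for other splits:

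| Split | 106 | 150 | 240 |
|---|---|---|---|
| 50/50 | 0.54 | 0.46 | 0.36 |
| 30/70 | 0.59 | 0.50 | 0.39 |
| 20/80 | 0.68 | 0.57 | 0.45 |
| 10/90 | 0.91 | 0.76 | 0.60 |

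The 240 column is a best case. People who entered by viral load or by being on ART belong to neither h.2.b group. The 150 is illustrative, not a figure from the plan.

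**6. How many can be classified.** Suppose k of the 134 later participants can be placed in a group, and all of the first 106 can. The unused share of classifiable data is then k/(106 + k): 24% if a quarter can be placed, 39% if half, 56% if all. It passes one half only when k exceeds 106, which is 106/134 = 79% of the later participants.

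**7. Group definitions.** Aim 5 H1 sets people who changed regimen or developed new resistance against people starting ART. Section h.2.b sets resistance switches against starts and all other switches. Someone who switched for side effects is in the first group under H1 and in the second under h.2.b.

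**The case against.** The strongest case for leaving the text alone is that Aim 5 is exploratory, is not a randomised comparison and makes no power claim, so an 80% power standard is the reviewer's choice. The 106 may be a data cut, or the people enrolled before eligibility widened, and a cohort of that kind could justify restricting the two-group contrast. The documents state neither explanation and exclude neither. This lowers the severity. It does not explain why the association analysis should stop at 106, or why an early cut should be the final answer.

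A larger set is no cure for small effects. At 30/70, a difference of 0.2 SD gives 0.2/√(1/31.8 + 1/74.2) = 0.94 standard errors with 106 and 0.2/√(1/72 + 1/168) = 1.42 with 240. Power is about 16% and 29%, so it would probably be missed either way.

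Three stronger readings are tempting, and the documents do not support them:
- A reader might infer that more than half of the trial's data are thrown away. The omission concerns Aim 5 only; no other aim is limited to 106.
- A reader might infer that the two-group comparison gains the full benefit of 240. That would require every later entrant to have started or changed ART, and a.2 admits other routes.
- A reader might infer that the 106 are shown to come from early sites under narrower criteria. Section c.4 allows such changes, and a.2 already lists being on ART as a route, but nothing dates any change or says which sites enrolled first. A difference is possible, not shown.

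**Conclusion.** The point stands as a minor one. The restriction to 106 is unexplained and leaves about 56% of the planned baseline records out of Aim 5. The cost to the association analysis is standard errors about 1.50 times those available from 240. The cost to the two-group comparison cannot be fixed from the documents. At an assumed 30/70 split it lies between almost nothing, if few later entrants can be classified, and the gap from 0.59 to 0.39 SD, if all can.

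These figures rest on 240 being enrolled, which is a plan and not a count, on a two-sided 5% test, and on the assumed splits. Whether the first 106 represent the whole trial is an open question. The efficacy result is not affected.

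**What to change.** Amend the Aim 5 paragraph of h.2.b as follows.

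1. Run the final association analysis on all randomised participants with a baseline assessment.
2. Run the two-group comparison on all who entered by starting or changing ART. First reconcile the groups in Aim 5 H1 with those in h.2.b, and state for each entry route in a.2 whether it is assigned to a group or excluded.
3. Keep the 106-person run as an interim description, labelled as such. State its cut-off and the reason for it, and report site and enrolment period for both sets so that any difference can be seen.

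The cost is a short grouping rule, a revised paragraph and a re-run of the same analysis on data the trial collects anyway. No visit, measure or participant is added. The final Aim 5 result has to wait until enrolment closes.
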